7.2.1. Adverse Events

Adverse event definitions; assignment of severity, causality, action taken, and outcome; and procedures for reporting SAEs are detailed in [Appendix 1](#).

Subjects will be asked a non-leading HDYF? question such as “Have there been any changes in your health status since Screening/since you were last asked?” at the timepoints specified in [Appendix 4](#) (ie, at Screening [after the ICF is signed], at Check-in [Day -1], at each postdose vital sign measurement, and at an appropriate time for all other days). Subjects will also be encouraged to voluntarily report AEs occurring at any other time through the EOS.

Adverse events, whether volunteered, identified by the subject’s responses to HDYF? inquiries, or noted on physical examination, ECG, vital sign measurements, or clinical laboratory evaluations, will be recorded throughout the study (ie, from signing of the ICF until EOS [or ET if the subject discontinues from the study and does not complete a follow-up phone call]), either as subject medical history (if the event is reported as beginning prior to signing of the ICF or if the event occurs prior to study drug administration on Day 1 and is assessed as not related to study procedures by the Investigator [or designee]) or as AEs (if the event occurs after signing of the ICF but prior to study drug administration on Day 1 and is assessed as related to study procedures by the Investigator [or designee], or if the event occurs after study drug administration on Day 1 through EOT or ET regardless of relationship to study drug). From EOT or ET through EOS, only AEs assessed as related to study drug by the Investigator (or designee) are to be reported. All SAEs that develop from the time of ICF

signing until EOS (or ET, if the subject discontinues from the study and does not complete a follow-up phone call) are to be reported.

Unless a subject withdraws consent or is withdrawn from the study and does not complete the follow-up phone call, all subjects must be followed until EOS. Subjects with AEs that are assessed as related to study drug by the Investigator (or designee) which are ongoing at EOS may continue to be followed until the symptoms or value(s) return to normal, or acceptable levels, as judged by the Investigator (or designee) and confirmed by the Sponsor. The Investigator (or designee) should use appropriate judgment in ordering additional tests as necessary to monitor the resolution of events. The Sponsor may request that additional safety tests be performed.

Subjects will receive a follow-up phone call 7 days (\pm 2 days) after EOT or ET to determine if any SAE or drug-related AE has occurred since the EOT or ET visit.

At all times, a subject may be required to remain at the CRU for longer at the discretion of the Investigator (or designee).

Any event that meets the criteria of a suspected unexpected serious adverse reaction will be reported to the institutional review board (IRB) according to CRU policy by the Investigator (or designee) and to regulatory authorities by the Sponsor (or Sponsor designee) according to regulatory authority requirements. Refer to Reference Safety Information in the current IB¹ for pirtobrutinib for additional safety information.

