1.3.2. Pharmacokinetics

The summary of information is based on data generated from studies conducted using a reference pirtobrutinib tablet. As of September 30, 2020, PK data were available from 181 patients enrolled in the LOXO-BTK-18001 study. Steady-state PK parameters of

pirtobrutinib in these cancer patients could be derived from data collected on Cycle 1 Day 8 (Figure 1), and are shown in Table 3. These data show that pirtobrutinib is absorbed after oral administration with a median time to maximum observed plasma concentration (t_{max}) of approximately 2 hours and low clearance (Table 3). Due to the limited sampling interval (0 to 8 hours), imputation for the 24-hour sample was made from Cycle 1 Day 8 predose sample, leading to an estimated plasma half-life of approximately 20 hours. Maximum observed plasma concentration and area under the plasma concentration-time curve (AUC) of pirtobrutinib showed an increase proportional to dose (Figure 2). Following administration of the recommended Phase 2 dose 200 mg QD, mean trough plasma levels of pirtobrutinib exceeded the concentration required for 96% inhibition of BTK in vitro ($IC_{50} = \text{CCI}$
 $IC_{96} = \text{CCI}$). Further details may be found in the IB.¹

Pharmacokinetic data following oral administration of a 200-mg dose of pirtobrutinib in tablet form in healthy volunteers in the LOXO-BTK-20014 study indicate that there was little effect of either a standard meal or the proton pump inhibitor (omeprazole) on the PK of pirtobrutinib.

**Table 3: Pharmacokinetic Parameters of Pirtobrutinib in Cancer Patients
(Study LOXO-BTK-18001) at Steady State (Cycle 1 Day 8)**

Dose Level		max	max	0-8	0-24			Ratio AUC ₀₋₈ Day
25 mg QD								
50 mg QD								
100 mg QD								
150 mg QD								
200 mg QD								
250 mg QD								
300 mg QD								

Abbreviations:

AUC₀₋₂₄ = area

C_{max} = maximum

of subjects; QD = once daily; t_{1/2} = half-life; t_{max} = time of maximal plasma concentration.

^a N = 4, ^b N = 5, ^c N = 8, ^d N = 18, ^e N = 64, ^f N = 21, ^g N = 16, ^h N = 73

SDTM Transfer: September 30, 2020

CCI

CCI

optimization of the commercial site process, differences in the dissolution profiles were identified. Therefore, this study is designed to compare the PK of T2 tablets manufactured at the clinical trial site (reference [R]) and T2 tablets manufactured at the commercial site (test [T]) in healthy subjects.

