- e. 12-lead ECGs will be obtained at Screening and Check-in (Day -1), Day 1 (predose, and 2 and 4 hours postdose), Day 8 (predose, and 2 and 4 hours postdose), and Day 15 (168 hours postdose on Day 8 [EOT]) or ET. 12-lead ECGs will be collected after the subject has rested in the supine position for at least 10 minutes. When scheduled at the same time as PK blood draws, 12-lead ECGs will be obtained prior to and as close as possible to having blood drawn. The allowed sampling window for 12-lead ECGs is \pm 30 minutes from the nominal timepoint for all postdose 12-lead ECGs and no less than 10 minutes prior to dosing for predose 12-lead ECGs.
- f. Vital sign measurements (supine blood pressure and pulse rate) will be obtained at Screening, Check-in (Day -1), Day 1 (predose, and 2 and 4 hours postdose), Day 4 (72 hours postdose on Day 1), Day 8 (predose, and 2 and 4 hours postdose), Day 11 (72 hours on Day 8), and Day 15 (168 hours postdose on Day 8 [EOT]) or ET. Blood pressure and pulse rate will be measured using the same arm for each reading after the subject has been supine for at least 5 minutes. When scheduled at the same time as PK blood draws, vital sign measurements should be carried out prior to and as close as possible to having blood drawn. The allowed sampling window for vital sign measurements is \pm 30 minutes from the nominal timepoint for all postdose vital sign measurements and no less than 10 minutes prior to dosing for predose vital sign measurements.
- g. Respiratory rate, oxygen saturation, and body temperature will be obtained at Screening, Check-in (Day -1), and Day 15 (168 hours postdose on Day 8 [EOT]) or ET. Oxygen saturation will also be obtained at predose on Day 1. The allowed sampling window for oxygen saturation measurements is \pm 30 minutes from the nominal timepoint for all postdose oxygen saturation measurements and no less than 10 minutes prior to dosing for predose oxygen saturation measurements.
- h. A HDYF? inquiry will be performed at Screening (after the ICF is signed), at Check-in (Day -1), at each postdose vital sign measurement, and at an appropriate time for all other days.

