- m. Clinical chemistry panel (fasted for at least 8 hours), coagulation parameters, hematology panel, and UA will be performed at Screening, Check-in (Day -1), Day 4 (72 hours postdose on Day 1), Day 7 (144 hours postdose on Day 1), Day 11 (72 hours postdose on Day 8), and Day 14 (144 hours postdose on Day 8, if the subject completes the study [EOT]), or on the day of ET. At ET or the day before EOT (Day 14), subjects are not required to be fasted prior to clinical laboratory evaluations.

- n. Testing for COVID-19 will be conducted at a minimum at Screening and Check-in (Day -1). Testing for COVID-19 may also be conducted periodically during the subject's CRU confinement, at the discretion of the Investigator (or designee). Tests will be performed by rapid polymerase chain reaction or equivalent.
- o. Urine drug screen for selected drugs of abuse (including cotinine) and alcohol screen (urine or breath).
- p. Prior and concomitant medication administration will be recorded beginning at informed consent. In addition, all Investigator-approved prescription and over-the-counter medications taken by a subject within 14 days or 5 half-lives (if known), whichever is longer, prior to Day 1 will be recorded on the subject's electronic case report form.
- q. Female subjects only. Performed at Screening, Check-in (Day -1), and Day 14 (144 hours postdose on Day 8), if the subject completes the study (EOT) or on the day of ET.
- r. Post-menopausal female subjects only.
- s. End of Treatment is defined as when the subject is released from the CRU following completion of all assessments through Day 15. Early Termination is defined as when the subject is released from the CRU if the subject terminates the study early. Vital sign measurements, ECG, and abbreviated physical examination results are to be available for review by the Investigator (or designee) prior to subject release from the CRU on Day 15 (EOT) or ET. Clinical laboratory results (for clinical chemistry, hematology, coagulation, and UA) and pregnancy test results (female subjects only) are to be available for review by the Investigator (or designee) prior to subject release from the CRU at the EOT visit and prior to subject release from the CRU at the ET visit, if available.

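### Non-serious AEs not judged related are recorded only until the subject leaves the unit: 168 h after the last dose for completers, but with no stated minimum for subjects who terminate early

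*Protocol*

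**What the plan says.** Protocol Section 7.2.1 classes an event as an AE "if the event occurs after study drug administration on Day 1 through EOT or ET regardless of relationship to study drug". After that point the rule narrows: "From EOT or ET through EOS, only AEs assessed as related to study drug by the Investigator (or designee) are to be reported". Serious events are treated differently. The sentence beginning "All SAEs that develop from the time of ICF" carries no relatedness condition and runs to End of Study (EOS), or to ET if a subject who discontinues does not complete the call. The same rules appear in the protocol synopsis, Section 3.1, Appendix 4 note i and SAP Section 4.

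Both end points are defined by leaving the unit. Appendix 4 note s says "End of Treatment is defined as when the subject is released from the CRU following completion of all assessments through Day 15" and "Early Termination is defined as when the subject is released from the CRU if the subject terminates the study early". For completers the timing is fixed, as the assessment notes in Appendix 4 show: "Day 15 (168 hours postdose on Day 8 [EOT]) or ET". For ET no minimum time after the last dose is given; Section 7.2.1 lets the Investigator keep a subject longer but does not require it.

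Every dosed subject, including early terminators, is due a call 7 ± 2 days after EOT or ET (Section 7.2.1; Appendix 4 note t). Its stated purpose is "to determine if any SAE or drug-related AE has occurred since the EOT or ET visit".

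**The concern.** The any-cause window is tied to leaving the unit rather than to the last dose. For completers the two amount to the same thing. For early terminators they do not, so the same non-serious event at the same time after dosing can be recorded in a subject still in the unit and go unreported in one who has left.

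This bears on the secondary objective, the safety and tolerability of each tablet lot. Both documents define a TEAE without reference to causality (Protocol Appendix 1; SAP Section 8.6.1). The SAP tabulates all TEAEs by treatment, severity, system organ class and preferred term, and its safety population (Section 7.2) includes everyone dosed at least once. An early terminator is therefore a full member of the denominator with a possibly truncated event count, and nothing in the SAP flags or adjusts for this.

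After release, reporting depends on a causality judgement made in an open-label study, partly from a phone call. Under Protocol Appendix 1, an event is related only if its timing fits and no other cause can be identified. An event with fitting timing and a plausible alternative cause does not meet that definition, so it need not be reported once the subject has gone.

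**Working it through.** **Inputs.** Doses on Day 1 and Day 8, and EOT on Day 15 (Protocol Section 3.1). Call at 7 ± 2 days after EOT or ET (Section 7.2.1). Half-life: Section 1.3.2 describes patient data with a 24-hour value imputed from the predose sample, "leading to an estimated plasma half-life of approximately 20 hours". Up to 28 subjects (Section 8.1).

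**Step 1: the plan's own figure.** Last dose to EOT: (15 − 8) × 24 = 168 h, which matches Appendix 4. First dose to second dose: (8 − 1) × 24 = 168 h. A completer therefore has 168 h of any-cause recording after each dose.

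**Step 2: early terminators.** Let h be the time from last dose to release, 0 < h < 168. The any-cause window is h. The window for SAEs and related AEs runs to the call: h + 120 h at the earliest, h + 168 h nominally, h + 216 h at the latest. The last column applies the proposed rule, the smaller of 168 h and the time of the call. The release times are illustrative; the documents give no distribution of ET times.

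| Release (h after last dose) | Any-cause window now | Share of 168 h | SAE and related-AE window: earliest / nominal / latest call | Any-cause window under the fix |
|---|---|---|---|---|
| 4 | 4 h | 2% | 124 / 172 / 220 h | 124 to 168 h |
| 24 | 24 h | 14% | 144 / 192 / 240 h | 144 to 168 h |
| 72 | 72 h | 43% | 192 / 240 / 288 h | 168 h |
| 144 | 144 h | 86% | 264 / 312 / 360 h | 168 h |
| 168 (completer) | 168 h | 100% | 288 / 336 / 384 h | 168 h (unchanged) |

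**Step 3: does the existing call reach far enough?** The earliest permitted call falls before 168 h when h + 120 < 168, that is, when h < 48. A flat requirement of 168 h could then run past the call, which is itself EOS. Hence the proposed window closes at 168 h or at the call, whichever comes first. The window under the fix is always more than 120 h.

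**Step 4: exposure at release.** Assuming mono-exponential decline with a 20 h half-life, the fraction remaining is 2^(−24/20) = 0.435 at 24 h and 2^(−168/20) = 0.003 at 168 h (168/20 = 8.4 half-lives). Narrowing to related events is easy to defend at 168 h and less so at 24 h.

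**Step 5: effect on a table.** With 28 subjects on a treatment, one subject whose event is missed changes an incidence by 1/28 = 3.6 percentage points. This is the size of one miss, not an expected loss: the documents give neither an ET rate nor an AE rate.

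**The case against.** The strongest case against is that very little is lost, and most of that case stands.

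- A reader might infer that early terminators are watched for only hours. The documents do not support that as a general statement. It is the extreme of a range that reaches almost 168 h, and there may be few or no early terminators.
- A reader might infer that safety follow-up stops at release. It does not. SAEs of any cause and related AEs are collected to the call, and Section 7.2.1 encourages voluntary reporting through EOS. SAE and related-AE coverage is lost only if a subject who discontinues does not complete the call.
- A reader might infer that the events that make subjects leave are the ones lost. An event that prompts withdrawal begins before release and is recorded whatever its cause. ET assessments are also to be attempted (Section 4.6; Appendix 4). Only a new, later, non-serious event can be missed.
- Appendix 1 calls an event not related only when timing rules the drug out and another cause is suspected, and it also refers to a reasonable possibility. Substantial remaining drug makes timing hard to use against causality. That weakens the worry but does not remove it, because the related category still requires that no other cause can be identified.
- The rule is worded consistently throughout and contradicts nothing. It is a design choice, and the safety analysis is descriptive only (SAP Section 8.6.6).

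What remains is a real difference in any-cause recording between completers and early terminators within the same TEAE tables.

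**Conclusion.** The point holds in a limited form. Non-serious AEs not judged related are recorded for 168 h after the last dose in completers and for an unspecified time, anywhere from just above 0 to just under 168 h, in early terminators. The consequence is possible under-counting in the descriptive by-treatment TEAE summaries, at 3.6 percentage points per missed subject with 28 on a treatment. It arises only if someone terminates early and then has a new non-serious event that is not judged related; the documents do not allow that probability to be estimated.

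A reader might go further and doubt the comparison of the two lots as a whole. The documents do not support that: the primary PK analysis and the sample size do not use AE data, and no inferential safety analysis is planned. This is a cheap improvement rather than a flaw that threatens the trial. The window lengths rest on the protocol's day numbering alone; only the exposure figures depend on the 20 h patient half-life and mono-exponential decline.

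**What to change.** In Protocol Section 7.2.1 and its copies (synopsis, Section 3.1, Appendix 4 note i, SAP Section 4), state that for dosed subjects who terminate early, all AEs regardless of relationship are recorded through 168 h after the last dose or the follow-up call, whichever is earlier; from then to EOS, the present rule for related AEs and SAEs applies. Change the description of the call in Section 7.2.1 and Appendix 4 note t so that, for these subjects, it asks about all AEs with onset in that window. Completers are unchanged.

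The cost is protocol and SAP wording and a changed question in a call already planned for every dosed subject; no visit or sample is added. Three limits remain: some events in early terminators will rest on phone recall; the window may end between 120 and 168 h when release is under 48 h after the dose and the call falls early; and subjects who miss the call are still not covered.

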7.2.2. Clinical Laboratory Evaluations

Clinical laboratory evaluations (clinical chemistry panel [fasted at least 8 hours; at ET or the day before EOT, subjects are not required to be fasted prior to clinical laboratory evaluations], coagulation parameters, hematology panel, TSH [Screening only], HbA1c [Screening only], CrCl [Screening and Check-in (Day -1)], and UA) will be collected at the timepoints specified in [Appendix 4](#).

Screens for HCV antibody, HBsAg, HBV IgM core antibody, and HIV antibody will be performed at Screening.

Testing for COVID-19 via PCR (or equivalent) will be performed at the timepoints specified in [Appendix 4](#). Testing for COVID-19 may also be conducted periodically during the subject's CRU confinement, at the discretion of the Investigator (or designee). Further details regarding COVID-19 testing (including procedures for subjects who test positive at any time throughout CRU confinement) are specified in a separate document.

A urine drug screen for selected drugs of abuse (including cotinine) and an alcohol screen (urine or breath) will be performed at Screening and repeated at Check-in (Day -1) for all subjects. A serum qualitative or urine qualitative pregnancy test (female subjects only [quantitative serum human chorionic gonadotropin tests may be used for confirmation as needed and post-menopausal subjects may be eligible for participation if the results of the qualitative serum pregnancy or qualitative urine pregnancy test are positive but the quantitative serum human chorionic gonadotropin results are within the laboratory's

reference ranges for post-menopausal women]) and an FSH test (post-menopausal female subjects only) will be performed at the timepoints specified in [Appendix 4](#).

The number of blood samples and total blood volume required for clinical laboratory evaluations are presented in [Appendix 3](#). A list of the specific evaluations is in [Appendix 2](#).

7.2.3. Vital Signs

Vital sign measurements (including body temperature, respiratory rate, oxygen saturation, and supine BP and pulse rate) will be obtained at the timepoints specified in [Appendix 4](#).

Blood pressure and pulse rate measurements should be performed using the same arm for each reading and measurements should be taken after the subject has been resting in the supine position for at least 5 minutes.

When vital sign measurements are scheduled at the same time as PK blood draws, the PK blood draws will be obtained at the scheduled timepoint, and the vital sign measurements will be obtained prior to and as close as possible to the scheduled PK blood draw.

7.2.4. 12-lead Electrocardiogram

A 12-lead ECG (including HR, PR, RR, QRS, and QT interval parameters) will be obtained after the subject has been resting for at least 10 minutes in the supine position at the timepoints specified in [Appendix 4](#). The QT interval will be corrected for HR by Fridericia's ($QTcF = QT/[RR]^{1/3}$) formula.

When 12-lead ECGs are scheduled at the same time as PK blood draws, the PK blood draws will be obtained at the scheduled timepoint, and the 12-lead ECGs will be obtained prior to and as close as possible to the scheduled PK blood draw.

7.2.5. Physical Examination

A complete or abbreviated physical examination will be performed at the timepoints specified in [Appendix 4](#). Complete physical examinations will evaluate general appearance and the following body systems/organs: dermatological; head and eyes; ears, nose, mouth, and throat; pulmonary; cardiovascular; abdominal; lymphatic; musculoskeletal/extremities; and neurological. Weight and height will be reported (height only reported during Screening). Abbreviated physical examinations will evaluate general appearance and the following body systems/organs: dermatological; pulmonary; cardiovascular; abdominal; and neurological.

8. SAMPLE SIZE AND DATA ANALYSIS

8.1. Determination of Sample Size

Up to 28 healthy adult male and female subjects (women of non-childbearing potential only) will be enrolled. This is a relative bioavailability study; however, a total of 28 evaluable subjects (14 subjects per treatment sequence) will provide at least 81% power to have the respective 90% confidence intervals (CIs) for the geometric mean ratios for C_{max} and AUC values between test and reference lot tablets are within the interval of 80.00% to 125.00%,

assuming a within subject coefficient of variation (CV) of 25% and that the expected ratio of means is 1.05 (or 0.95). Based on PK results of LOXO-BTK-20009, CV% of AUC is around 25%. Replacement subjects may be enrolled only if deemed necessary by the Sponsor. Every attempt will be made to enroll at least 3 subjects of each sex in the study.

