4.5. Subject Number and Identification

Subject numbers will consist of 6 digits in which the first set of 3 digits will identify the site and the second set of 3 digits will identify the subject (eg, 001-101).

For subjects who are withdrawn by the Investigator (or designee) or voluntarily withdraw prematurely from the study, replacement subjects will be enrolled only if deemed necessary by the Sponsor.

If necessary, as determined by the Sponsor, subjects who fail to complete the treatment or have insufficient PK data may be replaced. Replacement subjects will be assigned a subject

number by adding 200 to the last 3 digits of the subject number for the subject they are replacing (eg, Subject Number 001-301 replaces Subject Number 001-101).

Subjects who are determined to be screen failures are permitted to be re-screened if the Investigator (or designee), with agreement from the Sponsor, feels that the subject may meet eligibility criteria upon re-screen. Re-screened subjects will be provided a new subject number as defined above. A minimum of 7 days must elapse between date of screen failure and date of re-screening.

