8.2. Analysis Populations

8.2.1. Pharmacokinetic Population

The PK population will include all subjects who have received a dose of study drug, have at least 1 quantifiable plasma concentration, and for whom at least 1 PK parameter can be computed. A subject may be excluded from the PK summary statistics and statistical analysis if the subject has an AE of vomiting that occurs on or before t_{max} . The impact of protocol deviations on the PK population will be evaluated on a case-by-case basis.

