5. SAMPLE SIZE JUSTIFICATION

Up to 28 healthy adult male and female subjects (women of non-childbearing potential only) will be enrolled. This is a relative bioavailability study; however, a total of 28 evaluable subjects (14 subjects per treatment sequence) will provide at least CCI power to have the respective 90% confidence intervals (CIs) for the geometric mean ratios for C_{max} and AUC values between test and reference lot tablets are within the interval of 80.00% to 125.00%, assuming a CCI and that the expected ratio of means is 1.05 (or 0.95). Based on PK results of LOXO-BTK-20009, CCI

■ Replacement subjects may be enrolled only if deemed necessary by the Sponsor. Every attempt will be made to enroll at least 3 subjects of each sex in the study.

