8.5.3. Pharmacokinetic Statistical Methodology

A statistical analysis will be conducted to investigate the relative bioavailability of 200 mg pirtobrutinib test lot tablets (test treatment) versus 200 mg pirtobrutinib reference lot tablets (reference treatment).

The hypothesis testing will be 2-sided and carried out on 0.1 significance level.

The natural log (ln)-transformed⁴ AUC_{0-t} , AUC_{0-inf} , and C_{max} (only for plasma pirtobrutinib) will be analyzed using a mixed model.⁵ The model will include planned treatment sequence, period, and actual treatment as fixed effects, and subject within planned treatment sequence as a random effect.

For each PK parameter separately, the least squares mean (LSM) for each treatment, difference in LSMs between the test and reference treatments, and corresponding 90% CI will be calculated; these values will then be back-transformed to give the geometric least square mean (GLSM), geometric mean ratio (GMR), and corresponding 90% CI.

It will be concluded that the test treatment is bioequivalent to the reference treatment if, for all tested PK parameters, the 90% CI for GMR is completely contained within the predefined interval of (80.00%, 125.00%).⁶ This procedure is equivalent to Schuirmann's⁷ two one-sided tests at the 0.05 level of significance.

Additionally, the pooled estimate (across treatments) of the within-subject CV will be calculated, and residual plots will be produced to assess the adequacy of the model(s) fitted.

Examples of the SAS code that will be used are as follows:

Mixed Model Analysis

```
proc mixed data = <data in>;
```

```
by parcat1n parcat1 pkday paramn param;
class trtan aperiod trtseqp usubjid;
model lpk = trtan aperiod trtseqp / cl residual ddfm = kr;
lsmeans trtan / cl pdiff = control('1') alpha = 0.1;
random intercept / subject = usubjid(trtseqp);
ods output lsmeans = <data out>;
ods output diffs = <data out>;
ods output covparms = <data out>;
run;
```

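### Does enrolling up to 28 subjects, the same 28 evaluable subjects that the power statement needs, leave the stated 81% unsupported?

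*Protocol*

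**What the plan says.** Protocol 8.1 sets the size of the trial in two statements: "Up to 28 healthy adult male and female subjects (women of non-childbearing potential only) will be enrolled", and "a total of 28 evaluable subjects (14 subjects per treatment sequence) will provide at least 81% power". The target is that the 90% confidence intervals for the geometric mean ratios "are within the interval of 80.00% to 125.00" per cent, with a within-subject CV of 25% and an expected ratio of 1.05 (or 0.95). SAP 5 repeats the condition with its power figure blacked out: "a total of 28 evaluable subjects (14 subjects per treatment sequence) will provide at least CCI power".

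On loss of subjects, Protocol 8.1 says "Replacement subjects may be enrolled only if deemed necessary by the Sponsor". Protocol 4.5 says who may be replaced: "If necessary, as determined by the Sponsor, subjects who fail to complete the treatment or have insufficient PK data may be replaced". It also gives a numbering rule that ties each replacement to the subject replaced. Protocol 8.2.1 names one route to loss: "A subject may be excluded from the PK summary statistics and statistical analysis if the subject has an AE of vomiting".

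SAP 8.5.3 attaches a decision to the intervals: "It will be concluded that the test treatment is bioequivalent to the reference treatment if, for all tested PK parameters", the interval lies wholly within the limits.

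**The concern.** The largest planned enrolment and the evaluable number behind the power statement are both 28. Neither document states a non-evaluable rate, an inflation factor or a minimum evaluable count. Yet the plan expects that some data may be lost. Besides the vomiting rule and the non-completers of Protocol 4.5, SAP 8.5.1.4 drops second-period data when the predose concentration exceeds 5% of Cmax, and SAP 8.1.1 foresees missed visits because of COVID-19. Replacement has no trigger tied to the evaluable count.

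Read this way, the stated power holds only if every loss is replaced, and nothing obliges the Sponsor to replace. At a ratio of exactly 0.95, even 28 evaluable subjects give slightly less than 81% before rounding. The stake would be a higher chance of an inconclusive result in a study that is called relative bioavailability but from which the SAP draws a bioequivalence conclusion.

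**Working it through.** **Inputs.** From Protocol 8.1: 28 evaluable subjects, 14 per sequence; within-subject CV 25%; true ratio 1.05 or 0.95; limits 0.80 and 1.25. From SAP 8.5.3: two one-sided tests at 0.05, equivalent to the 90% interval. From Protocol 3.1: two sequences, TR and RT, in a two-period crossover.

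**Formulas.**
- Within-subject SD on the log scale: sqrt(ln(1 + 0.25²)) = sqrt(ln 1.0625) = 0.2462.
- Standard error of the log ratio: 0.2462 × sqrt(0.5 × (1/n1 + 1/n2)). For 14 + 14 this is 0.2462 × sqrt(1/14) = 0.0658.
- Degrees of freedom: n1 + n2 − 2 = 26, with t(0.95, 26) = 1.706.
- Power: the probability that the estimate ± t × estimated standard error stays within ±ln 1.25 = ±0.2231, integrated over the chi-square distribution of the residual variance.

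**The plan's own figure.** With 14 + 14 evaluable, power is 81.63% at 1.05 and 80.74% at 0.95. A simulation with 400,000 replicates gave 81.8% and 80.8%. The stated 81% is reproduced.

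The gap between the two ratios comes from how 0.95 is read. The limits are symmetric on the log scale, so the mirror image of 1.05 is 1/1.05 = 0.952, which prints as 0.95. At 0.952 the power is 81.63%, the same as at 1.05. Only at exactly 0.9500 is it 80.74%, which still rounds to 81%. The documents do not say which was meant.

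**Cost of unreplaced losses** (power for one parameter, CV 25%):

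| Evaluable (by sequence) | Ratio 0.95 | Ratio 1.05 or 1/1.05 |
|---|---|---|
| 28 (14+14) | 80.7% | 81.6% |
| 27 (14+13) | 79.2% | 80.1% |
| 26 (13+13) | 77.6% | 78.5% |
| 25 (13+12) | 75.8% | 76.7% |
| 24 (12+12) | 73.9% | 74.8% |
| 26 (14+12) | 77.4% | 78.3% |
| 25 (14+11) | 75.2% | 76.1% |
| 24 (14+10) | 72.6% | 73.5% |

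With losses spread over both sequences, each costs about 1.5 to 2 points: from 28 to 27 at 1.05, 81.6 − 80.1 = 1.5; from 25 to 24, 76.7 − 74.8 = 1.9. Losses that all fall in one sequence cost somewhat more. At a true ratio of 1.00, power is 90.2% with 28 and 83.7% with 24.

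**The power statement beside the replacement rule.** Protocol 8.1 promises 81% for 28 evaluable subjects, not for whatever number remains out of 28 enrolled. Protocol 4.5 gives a way back to 28 when someone drops out or lacks PK data. The two fit together. What is left open is when the Sponsor would use the mechanism.

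**The case for a change.** The best case for a change is that discretion is not commitment. The first number is a ceiling, so 28 is the best outcome unless replacements are added on top, and the text does not say whether they count within it. The test lot was chosen for its slower dissolution (Protocol 2.1.1), so a ratio below 1 is plausible, and 0.95 is the less favourable of the two scenarios. At exactly 0.95 one unreplaced loss takes power to 79.2%, and the smallest evaluable number that reaches 81% at both ratios without rounding is 29 (82.1% and 83.0%). Committing to replacement would take a sentence.

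The arithmetic in that case stands, as does the absence of a trigger. The rest is weaker:

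- Neither document sets 80% as a threshold, so falling below it misses no stated target.
- The call for 29 rests on reading 0.95 as exactly 0.9500.
- Saying that the power holds only if all 28 enrolled subjects are evaluable would be less accurate than the present text, because replacements can restore the count.
- Mandatory replacement means dosing more healthy volunteers to recover 1.5 to 2 points each, and it removes a choice that the Sponsor can reasonably make once the actual loss is known.
- The exposure looks limited. Subjects stay in the unit from Day -1 to Day 15 and take two supervised doses. Protocol Table 2 lists three treatment-related vomiting reports across the earlier clinical pharmacology studies, some of which gave up to 900 mg. This is not a loss rate, and none can be derived from the documents.

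**Conclusion.** No change is needed. The 81% figure is right to rounding, its condition is already written beside it, and a replacement route exists for the subjects whose loss would matter. Leaving the trigger to the Sponsor is a fair trade-off between a small amount of power and dosing further volunteers.

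If losses are not replaced, power for one parameter falls to 79.2–80.1% with 27 evaluable subjects and 73.9–74.8% with 24 split equally. The consequence is a wider interval and a greater chance of an inconclusive result. The two one-sided tests keep their 0.05 level at any evaluable number, so the risk of a false claim of bioequivalence does not rise.

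This rests on the protocol's CV of 25% and ratios of 1.05 or 0.95, on reading the power as applying to each parameter separately, and on counting a subject as evaluable only with usable data in both periods. The power and CV in SAP 5 are blacked out and could not be compared. If the protocol is amended for other reasons, a note that the 28 may include replacements under Section 4.5, and when replacement would be considered, would be a courtesy to the reader.
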